7 ABBREVIATIONS

~	Approximately
Mg	Micrograms
AE	Adverse event
ALP	Alkaline phosphatase
ALT	Aspartate aminotransferase
aPTT	Activated prothrombin time
AST	Alanine aminotransferase
AM	Arithmetic mean
ANOVA	Analysis of variance
AUC	Area under the concentration-time curve
AUC%extrap	Percent of AUC _{0-inf} extrapolated
AUC ₀₋₂₄	Area under the concentration-time curve, from time 0 to 24 hours post dose
AUC _{0-t}	Area under the concentration-time curve, from time 0 to the last observed non-zero concentration (t)
AUC _{0-inf}	Area under the concentration-time curve, from time 0 extrapolated to infinity
BID	Twice daily
BCRP	Breast Cancer Resistance Protein
bpm	Beats per minute
BMI	Body mass index
°C	Degrees Celsius
CFR	Code of Federal Regulations
CI	Confidence interval
cm	Centimeter
C _{max}	Maximum observed concentration
CRF	Case report form
CRU	Clinical Research Unit
CV	Coefficient of variation
CYP	Cytochrome P450
DNA	Deoxyribonucleic acid
ECG	Electrocardiogram

FDA	Food and Drug Administration
FSH	Follicle-stimulating hormone
g	Gram
GCP	Good Clinical Practice
GLP	Good Laboratory Practice
HBsAg	Hepatitis B surface antigen
hERG	Human ether-a-go-go related gene
HCV	Hepatitis C virus
HIV	Human immunodeficiency virus
ICF	Informed Consent Form
ICH	International Council for Harmonisation
IND	Investigational New Drug
INR	International normalized ratio
IRB	Institutional Review Board
Kel	Apparent terminal elimination rate constant
kg	Kilogram
LSM	Least-squares means
m^2	Meters squared
MedDRA®	Medical Dictionary for Regulatory Activities®
mg	Milligram
mL	Milliliter
mmHg	Millimeter of mercury
msec	Millisecond
n	Sample size
No.	Number
OATP	Organic anion-transporting polypeptide
oz	Ounce
P-gp	P-glycoprotein
PI	Principal Investigator
PK	Pharmacokinetic(s)
PT	Prothrombin time
RNA	Ribonucleic acid

QA	Quality Assurance
QD	Daily
QTc	QT interval corrected for heart rate
SAE	Serious adverse event
SAP	Statistical analysis plan
SD	Standard deviation
Tmax	Time to reach maximum observed concentration
t½	Apparent terminal elimination half-life
US	United States
USA	United States of America
WHO	World Health Organization

8 INTRODUCTION

8.1 Background

8.1.1 LOXO-292

LOXO-292 is a small molecule and a selective inhibitor of the RET receptor tyrosine kinase designed to competitively block the adenosine triphosphate binding site of the kinase. LOXO-292 was at least 250-fold more selective for RET than for 98% of 329 other kinases tested in a large in vitro screen. Consistent with such a high degree of selectivity, LOXO-292 caused significant cytotoxicity in human cancer cell lines that harbored endogenous, clinically relevant RET gene alterations but was much less cytotoxic against human cancer cell lines without RET alterations. Potent and selective inhibition of RET may provide clinical benefit to subjects with malignancies due to oncogenic alterations in RET or with other mechanisms of increased RET activity.

Nonclinical

Cardiac safety of LOXO-292 was evaluated in a Good Laboratory Practice (GLP) in vitro assay for human ether-a-go-go related gene (hERG) activity, in a GLP in vivo study in conscious telemetry-instrumented minipigs, and in a GLP 28-day repeat-dose toxicology study (with ECG monitoring) in minipigs. LOXO-292 had an IC_{50} value of 1.1 μM in the GLP hERG assay, which is approximately 17- and 9-fold higher than the predicted maximum unbound concentration at the clinical dose of 80 mg and 160 mg respectively twice daily (BID). There were no LOXO-292-related changes in any cardiovascular endpoints including QT interval corrected for heart rate (QTc) at doses up to 12 mg/kg in the safety pharmacology cardiovascular study in conscious minipigs. Furthermore, there were no LOXO-292-related ECG changes in the 28-day repeat-dose toxicity study in minipigs at the high dose of 12 mg/kg. Together, these data indicate that LOXO-292 has a low risk of inducing delayed ventricular repolarization, prolongation of the QTc interval, and unstable arrhythmias.

Administration of LOXO-292 at single doses up to 45 mg/kg in male rats had no effect on respiratory function.

Potential effects of LOXO-292 on the central nervous system were evaluated as part of the GLP 28-day repeat-dose study in rats, in functional observational battery tests and locomotor activity assessments. Findings were limited to animals receiving the high dose on week 4 of the dosing phase, and were attributed to poor general body condition and weight changes associated with LOXO-292 administration rather than specific neurological effects. Additionally, no microscopic abnormalities in neuronal tissues were found.

In toxicology studies of LOXO-292 that were conducted in the rat and minipig, the primary pathologic findings for both species were in the tongue, pancreas, bone marrow and lymphoid tissues; while the gastrointestinal tract and ovaries were target tissues in minipig. Other target tissues identified in the rat included: multi-tissue mineralization, phyeal cartilage, incisor teeth, lung, Brunner's gland, and possibly liver. Assessment of doses associated with moribundity/death revealed a steep dose response curve for both species.

LOXO-292 was not mutagenic in the GLP bacterial mutation assay. LOXO-292 was not found to be phototoxic when evaluated in an in vitro neutral red uptake phototoxicity assay.

Based on preclinical pharmacology experiments with human cancer cells in vitro and in murine xenograft models, meaningful inhibition of RET in tumors is expected to be achievable with oral dosing regimens ≥ 40 mg/day.

Based on the nonclinical profile, including results from animal toxicology studies, theoretical risks of human exposure to LOXO-292 include the following: loss of appetite, decrease in body weight, increase in total white blood cells, neutrophils, and monocytes, decrease in albumin, increase in globulin, decreased albumin:globulin ratio, decrease in total protein, increased body temperature, lethargy, increase in cholesterol and triglycerides, increase in phosphorus, changes in taste sensation and/or development of xerostomia, gastrointestinal symptoms/signs: nausea, vomiting, loose stools, abdominal discomfort, decreases in red cell mass (red blood cells, hemoglobin, hematocrit) and reticulocytes, decrease in platelets, increases in liver function tests (alkaline phosphatase, aspartate aminotransferase and alanine aminotransferase).

LOXO-292 has been given orally and intravenously to mice, rats, dogs, minipigs, and monkey. LOXO-292 was absorbed and bioavailable in all species tested. Solubility studies and pharmacokinetic studies suggest that the pharmacokinetic exposure of LOXO-292 may be reduced by proton pump inhibitors and other antacids. LOXO-292 appears to be metabolized primarily by CYP3A4, but at therapeutically relevant exposures, it is not anticipated to inhibit or induce drug-metabolizing enzymes. LOXO-292 is also a substrate for BCRP.

Refer to the Investigator's Brochure for detailed background information on LOXO-292 [[Investigator's Brochure 2018](#)].

Clinical

LOXO-292 is currently being studied in an ongoing global Phase 1 first in human Study LOXO-RET-17001 in patients with advanced solid tumors including RET fusion-positive NSCLC, RET-mutant MTC, and other tumors with increased RET activity. The starting dose of LOXO-292 was 20 mg once daily. As of a January 5, 2018 data cut-off date, safety data was available from 57 patients with 160 mg BID as the highest dose administered. As of January 5, 2018, no dose-limiting toxicities have been reported. TEAEs occurring in $\geq 10\%$ of patients were: fatigue (16%), diarrhea (16%), and dyspnea (12%). The majority of TEAEs were Grades 1 or 2 and no \geq Grade 3 TEAEs were related to study drug. Three subjects have died during the study, and no deaths have been attributed to study drug.

Loxo Oncology has also initiated 3 IRB-approved, FDA-allowed single patient protocols (LOXO-RET-17002, LOXO-RET-17003 and LOXO-RET-17004) to provide access to LOXO-292 for patients with clinical need not meeting eligibility criteria for the ongoing clinical study. As of January 5, 2018, no TEAEs have been attributed to study drug for these patients.

As of February 9, 2018, PK were available from patients (from the LOXO-RET-17001 study); LOXO-292 is absorbed after oral administration with a time to maximum concentration (Tmax) of approximately 2 hours. Although the pharmacokinetic sampling of LOXO-292 was not long to adequately characterize AUC0-inf, the half-life was estimated to be at least 12 hours or longer. Low concentrations of LOXO-292 were recovered as unchanged drug in urine indicates that the kidney contributes to overall clearance.

8.1.2 Itraconazole

Itraconazole is an azole antifungal agent. Starting doses of itraconazole capsules vary by indication and range from 200 mg QD to 200 mg twice daily. The capsule formulation should be taken with food to maximize its absorption.

Itraconazole is rapidly absorbed after oral administration. Peak plasma concentrations of itraconazole are reached within 2 - 5 hours following a single oral dose of the capsule. The observed absolute oral bioavailability of itraconazole is approximately 55%.

Itraconazole is metabolized predominantly by the CYP3A4 enzymes, and is known to undergo enterohepatic recirculation. Hydroxy-itraconazole is the major metabolite and shows antifungal activity equal to that of the parent. Itraconazole is a competitive CYP3A4 inhibitor, and following multiple dosing, approximately (~)40% of overall CYP3A inhibition is attributed to hydroxyl-itraconazole. In a clinical study, itraconazole (200 mg QD for 4 days) resulted in a ~10-fold increase in midazolam exposure, a CYP3A substrate. Itraconazole is also P-gp inhibitor, and 200 mg QD itraconazole for 5 days increased oral digoxin AUC by ~1.7 fold.

The terminal half-life of itraconazole typically ranges from 16 - 28 hours after a single dose and increases to 34 - 42 hours with multiple dosing, due to non-linear PK. Itraconazole is mainly excreted as inactive metabolites in the urine (35%) and feces (54%). Overall, itraconazole is associated with infrequent mild adverse reactions.

Overall, itraconazole is associated with infrequent mild adverse reactions. The potential risks in healthy subjects are low and manageable, and will be monitored during the study by serial monitoring of 12-lead ECGs, vital sign measurements, clinical laboratory tests, AEs, and physical examinations.

Itraconazole is classified as Food and Drug Administration (FDA) pregnancy category C.

For more information, refer to itraconazole labelling [[itraconazole capsules; Mylan Pharmaceuticals Inc.](#)].

8.1.3 Rifampin

Rifampin is a semi-synthetic antibiotic derivative of rifamycin SV which acts by inhibiting deoxyribonucleic acid (DNA)-dependent ribonucleic acid (RNA) polymerase activity in susceptible species of *Mycobacterium tuberculosis*. Its activity does not impede mammalian enzyme RNA polymerase, therefore it is an effective treatment for both tuberculosis and meningococcus infections.

After oral administration, rifampin is readily absorbed from the gastrointestinal tract and is considered to be a highly variable drug in healthy adults and pediatric populations. Gastric absorption with food reduces the bioavailability of rifampin by about 30%. Concomitant antacid administration may also reduce the absorption of rifampin. Thus, daily doses of rifampin should be given at least 1 hour before the ingestion of antacids, and 1 hour before or 2 hours after a meal.

Rifampin is widely distributed throughout the body and can reach effective concentrations in various organs and cerebrospinal fluid. Rifampin is 80% protein bound in the blood while the remaining unbound fraction is not ionized and can readily diffuses into tissues.

In healthy adults, the mean biological $t_{1/2}$ of rifampin in serum averages 3.35 ± 0.66 hours after a 600 mg oral dose, with increases up to 5.08 ± 2.45 hours reported after a 900 mg dose. With repeated administration, the $t_{1/2}$ decreases and reaches average values of approximately 2 -3 hours. The half-life does not differ in patients with renal failure at doses not exceeding 600mg daily, and consequently, no dosage adjustment is required. After a single 900 mg oral dose of rifampin in patients with varying degrees of renal insufficiency, the mean $t_{1/2}$ increased from 3.6 hours in healthy adults to 5.0, 7.3, and 11.0 hours in patients with glomerular filtration rates of 30 to 50 mL/min, less than 30 mL/min, and in anuric patients, respectively.

After absorption, rifampin is rapidly eliminated in the bile, and an enterohepatic circulation ensues. During this process, rifampin undergoes progressive deacetylation to form the desacetyl rifampin metabolite, and nearly all the drug in the bile is in this form by ~6 hours. This metabolite has antibacterial activity. Intestinal reabsorption is reduced by deacetylation, and elimination is facilitated. With dosages of 300 - 450 mg, the excretory capacity of the liver becomes saturated and increasing the dose results in a more than proportional increase in drug concentrations. Up to 30% of a dose is excreted in the urine, with about half of this being unchanged drug.

Rifampin, when acutely dosed, is an inhibitor of organic anion-transporting polypeptide (OATP) 1B1/1B36 and P-gp4 transporters. Following multiple dosing, rifampin is a potent inducer of drug metabolism by inducing a variety of hepatic and intestinal CYP enzymes, especially CYP3A4, and hepatic P-gp. Administration of rifampin with drugs that undergo biotransformation through these metabolic pathways may accelerate elimination of LOXO-292 coadministered drugs. To maintain optimum therapeutic blood levels, dosages of drugs metabolized by these enzymes may require adjustment when starting or stopping concomitantly administered rifampin. CYP induction by rifampin begins to plateau after 6 consecutive days of dosing, reaching a maximum by 8 - 9 days. However, due to the large interindividual variation in baseline CYP enzyme expression and polymorphisms, a reliable detection method is recommended to confirm enzyme induction by rifampin in each individual. The urinary ratio of 6β -hydroxycortisol to free cortisol is an efficient and effective method to detect CYP3A4 activity and urine samples will be collected in Part 2 of the study for future potential analysis to confirm CYP induction after single daily doses of rifampin.

Rifampin is classified as FDA pregnancy category C.

For more information, refer to the rifampin labelling [[rifampin capsules; Lannett Company Inc.](#)].

8.2 Rationale

8.2.1 Rationale for this Study and Study Design

Data from in vitro studies (human liver microsomes and human hepatocytes) indicate that LOXO-292 is a substrate of enzyme CYP3A4 and of P-gp transporters, thus rendering LOXO-292 susceptible to DDI when coadministered with inhibitors or inducers of CYP3A and/or P-gp.

Part 1:

Part 1 of the study will assess the effect of a strong CYP3A4 and P-gp inhibitor on the PK of LOXO-292. Itraconazole is a well characterized, competitive, strong inhibitor of CYP3A4 and a potent P-gp inhibitor; thus it was selected for this study as per recommendations in the FDA Guidance for Drug Interaction Studies [[FDA Oct 2017](#)]. Itraconazole capsules, when administered alone, will be administered under fed conditions to enhance oral absorption and to ensure that adequate plasma concentrations are attained for enzyme inhibition. When coadministered with LOXO-292; however, both drugs will be administered under fasting conditions, as the effect of food on the PK of LOXO-292 has not yet been evaluated. However, because this is the first time LOXO-292 is administered with a CYP3A4 inhibitor, Part 1 will include a sentinel group for safety purposes. This sentinel group will be composed of 3 subjects. Relevant safety and tolerability data will be evaluated before proceeding to dosing the remaining subjects in order to confirm such a dose can be given safely.

Part 2:

Part 2 of the study will assess the effect of a strong CYP3A4 and P-gp inducer on the PK of LOXO-292. Rifampin, administered as multiple doses, was selected as a CYP3A4/P-gp inducer for this study, in accordance to recommendations in the FDA Guidance for Drug Interaction Studies [[FDA Oct 2017](#)]. QD dosing of rifampin for 10 days has been reported to be adequate to attain maximal CYP3A enzyme induction [[Tran et al., 1999](#)]. Rifampin has also been shown in literature to be an effective inhibitor of P-gp in the gut when administered as an acute single dose. Thus, on Day 1 of Period 2, rifampin and LOXO-292 will be coadministered to evaluate the effect of P-gp inhibition on the PK of LOXO-292. All study drugs will be administered under fasting conditions in Part 2, as absorption of rifampin is reduced when it is administered with food [[rifampin capsules; Lannett Company Inc.](#)].

Part 1 and Part 2:

A fixed-sequence design has been selected in each study part. This design will reduce the study duration and prevent any carryover effects of itraconazole or rifampin on CYP enzymes and P-gp transporters by ensuring that each period is initiated with similar enzyme/transporter baseline levels. It is anticipated, based on limited multiple-dose data in cancer patients, that LOXO-292 exhibits a half-life of at least 12 hours however it may be as

long as 30 hours after a single dose; PK sampling will therefore be done up to 168 hours to ensure the adequate characterization of total exposure of LOXO-292 (i.e., 3 to 5 half-lives).

In both parts, the washout period between the LOXO-292 dose in Period 1 and the first dose in Period 2 is considered sufficient to prevent carryover effects of the treatment as it is greater than 7 half-lives of LOXO-292, if the half-life is up to 24 hours in duration.

8.2.2 Rationale for the Dose Selection and Dosing Regimen

LOXO-292:

A single dose of 160 mg LOXO-292 was selected because is a dose that has been given twice daily to cancer patients and preliminary safety and PK data show that this dose is likely at or near a recommended Phase 2 dose for further study in cancer patients. A single dose of 160 mg should provide sufficient levels of LOXO 292 to assess the PK properties being investigated.

LOXO-292 is a substrate of CYP3A4 and thus there may be an increase in the exposure (AUC) of LOXO-292 when it is given with the CYP3A4 inhibitor itraconazole. However, even if CYP3A4 is inhibited, LOXO-292 is expected to be eliminated from the body because LOXO-292 is also eliminated by renal excretion and renal excretion of LOXO-292 is unlikely to be affected by CYP3A4 inhibition. Renal clearance of LOXO-292 (as unchanged drug) is being evaluated in study LOXO-RET-17001. Interim analysis of data from 48 subjects in that study shows that a mean of approximately 8.4% of the oral dose was recovered in the urine as unchanged LOXO-292 (data on file, Loxo Oncology). Therefore, in the unlikely event that LOXO-292 were 100% absorbed and bioavailable, and its clearance were 100% inhibited by itraconazole, the body could clear the drug renally. Furthermore, as of a January 5, 2018 data cut-off date, safety data were available from 57 patients with doses up to 160 mg BID (320 mg/day). As of this date, no dose-limiting toxicities have been reported.

Itraconazole:

The clinical dose of itraconazole is 200 mg administered QD. In this study, itraconazole will be dosed for 11 days (Day -4 to Day 7), with LOXO-292 coadministered on the fifth day of itraconazole dosing. Although, itraconazole reaches steady-state at approximately 15 days QD dosing, similar dosing schemes have been used in previously reported DDI studies and have demonstrated sufficient inhibition of CYP3A enzymes with 5 days of QD dosing [Yoshizato et al., 2012]. To maintain the same level of inhibition, itraconazole will be administered throughout PK sampling of LOXO-292 until Day 7.

As itraconazole capsules should be administered with a full meal to maximize its absorption, dosing on Day -4 to Day -1 and Days 2 to 7 of Period 2 will be approximately 30 minutes after the start of a standard breakfast to maximize the inhibition potential. On Day 1 of Period 2, to assess the DDI under the most sensitive conditions, both study drugs will be administered under fasting conditions.

Rifampin:

The dose of rifampin selected for this study is 600 mg, which is commonly used in therapeutic regimens for adults for the treatment of tuberculosis. As per literature, an acute dose of rifampin inhibits P-gp-mediated transport while chronic dosing strongly induces CYP3A enzymes and P-gp [Shumaker et al., 2014]. Therefore, the acute (transporter) effect of rifampin on the single-dose PK of LOXO-292 will be assessed with a single oral dose to maximize the ability to observe small differences in PK. Sampling for 24 hours will be sufficient to evaluate the inhibitory effects as P-gp acts mostly in the gut (absorption/distribution phases). Rifampin dosing alone will then be continued QD to assess its induction potential on LOXO-292. The half-life of rifampin is ~3 hours following a 600 mg oral dose [rifampin capsules; Lannett Company Inc.]; however, the time required to produce maximum enzyme induction is substantially longer for the synthesis of new enzymes. The time frame from maximum induction by rifampin has been estimated at a minimum of 5 days of 600 mg QD [Tran et al., 1999]. In most, drug interaction studies, oral rifampin has typically been administered as a 600 mg QD dose for 4 - 18 days [Templeton et al., 2011]. To maximize induction of CYP3A4, 600 mg rifampin will be administered QD for 9 days prior to LOXO-292 coadministration on Day 10 of Period 2. Dosing will continue to Day 16 of Period 2 to maintain induction throughout the PK sampling time. Urine samples will be collected to potentially assess the urinary ratio of 6 β -hydroxycortisol to free cortisol. This ratio has been used historically to confirm CYP3A4 activity [Tran et al., 1999].

8.2.3 Rationale for Study Endpoints

The primary PK endpoints for Parts 1 and 2 will include AUC0-t, AUC0-24 (for Part 2, Day 1 PK only), AUC0-inf, and Cmax, as these parameters describe the exposure and bioavailability of LOXO-292 and are thought to be the most relevant PK parameters for the purpose of evaluating an interaction.

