10 STUDY DESIGN

10.1 Overall Study Design and Plan

This is a 2-part study. Each part will be conducted as an open label, 2-period, fixed-sequence study. Study parts may be conducted concurrently. Subjects will only participate in one study part.

CCI [REDACTED] healthy, adult male and female (women of non-childbearing potential only) subjects will be enrolled in total; CCI [REDACTED] to each study part (Parts 1 and 2). Every attempt will be made to enroll at least 4 subjects of each sex in each study part.

Screening of subjects will occur within 28 days prior to the first dosing.

Part 1 (Itraconazole):

On Day 1 of Period 1, a single oral dose of LOXO-292 will be administered followed by PK sampling for 168 hours.

In Period 2, an oral dose of itraconazole will be administered QD for 11 consecutive days (Day -4 to Day 7) with a single oral dose of LOXO-292 coadministered on Day 1. Pharmacokinetic sampling for LOXO-292 will be taken for 168 hours following LOXO-292 dosing on Day 1.

A CCI [REDACTED] will initiate Part 1; all subjects will receive a single dose of LOXO-292 on Day 1 of both periods. Following collection of the last PK sample in Period 2, the PI, in consultation with the Sponsor, will review all pertinent safety and tolerability data before proceeding to dose the remaining subjects.

Interim PK will be provided after completion of the sentinel group but it is not required for the dose selection of the remaining subjects.

There will be a washout period of at least 7 days between the dose in Period 1 and the first dose (i.e., itraconazole) in Period 2.

Safety will be monitored throughout the study.

Timing of all study procedures are indicated in the Study Events Flow Chart (Section 6, Table 1)

Part 2 (Rifampin):

On Day 1 of Period 1, a single oral dose of LOXO-292 will be administered followed by PK sampling for 168 hours.

In Period 2, an oral dose of rifampin will be administered QD for 16 consecutive days (Days 1 to 16) with a single oral dose of LOXO-292 coadministered on Day 1 and Day 10.

Pharmacokinetic sampling for LOXO-292 will be taken for 24 hours following LOXO-292 dosing on Day 1 and for 168 hours following LOXO-292 dosing on Day 10.

Morning urine will be collected on Days 1, 4, 8, and 10 of Period 2 (and will be stored for future potential assessment of 6 β -hydroxycortisol and free cortisol concentrations to evaluate the level of CYP3A enzyme induction).

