13.3.2 Plasma Pharmacokinetic Parameters

PK parameters for plasma LOXO-292 will be calculated as follows, as appropriate:

AUC0-24: The area under the concentration-time curve, from time 0 to the 24 hours postdose Day 1, as calculated by the linear trapezoidal method (for Part 2, Day 1 PK only).

AUC0-t:	The area under the concentration-time curve, from time 0 to the last observed non-zero concentration, as calculated by the linear trapezoidal method.
AUC0-inf:	The area under the concentration-time curve from time 0 extrapolated to infinity. AUC0-inf is calculated as the sum of AUC0-t plus the ratio of the last measurable plasma concentration to the elimination rate constant.
AUC%extrap:	Percent of AUC0-inf extrapolated, represented as $(1 - AUC0-t/AUC0-inf) * 100$.
Cmax:	Maximum observed concentration.
CL/F:	Apparent total plasma clearance after oral (extravascular) administration, calculated as Dose/AUC0-inf.
Tmax:	Time to reach Cmax. If the maximum value occurs at more than one time point, Tmax is defined as the first time point with this value.
Kel:	Apparent first-order terminal elimination rate constant calculated from a semi-log plot of the plasma concentration versus time curve. The parameter will be calculated by linear least-squares regression analysis using the maximum number of points in the terminal log-linear phase (e.g., three or more non-zero plasma concentrations).
t ^{1/2} :	Apparent first-order terminal elimination half-life will be calculated as $0.693/Kel$.

No value for Kel, AUC0-inf, or t^{1/2} will be reported for cases that do not exhibit a terminal log-linear phase in the concentration-time profile. The sampling to 24 hours for Day 1 PK in Period 2, Part 2 may not be sufficient for calculation of several Kel-dependent PK parameters.

No PK parameters will be calculated for subjects with 2 or fewer consecutive time points with detectable concentrations.

Individual and mean plasma concentration time curves (both linear and log-linear) will be included in the final report.

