14.3.1.3 Ratios and Confidence Intervals

Ratios of LSMS will be calculated using the exponentiation of the difference between treatment LSMS from the analyses on the ln-transformed AUC0-t, AUC0-24 (for Part 2, Day 1 PK only), AUC0-inf, and Cmax. These ratios will be expressed as a percentage relative to the appropriate reference treatment.

Consistent with the two one-sided tests [Schuirmann, 1987], 90% confidence interval (CI) for the ratios will be derived by exponentiation of the CIs obtained for the difference between treatment LSMS resulting from the analyses on the ln-transformed AUC0-t, AUC0-24 (for Part 2, Day 1 only), AUC0-inf, and Cmax. The CIs will be expressed as a percentage relative to the appropriate reference treatment.

The comparisons of interest are as follows:

- Treatment B compared with Treatment A [Part 1]
- Treatment D (Day 1 dosing) compared with Treatment C [Part 2]
- Treatment D (Day 10 dosing) compared with Treatment C [Part 2]

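### AUC0-inf remains a primary endpoint for the Part 2 single-dose rifampin comparison (Treatment D Day 1 vs C), although Day 1 sampling stops at 24 h and cannot give it reliably

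*Protocol*

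**What the plan says.** Section 8.2.3 sets the primary endpoints: "The primary PK endpoints for Parts 1 and 2 will include AUC0-t, AUC0-24 (for Part 2, Day 1 PK only), AUC0-inf, and Cmax". Section 9.2 lists AUC0-inf for Part 2 without restriction by day. Sections 14.3.1.2 and 14.3.1.3 apply the ANOVA, the ratio of least-squares means and the 90% CI to the same four parameters, and the comparisons of interest include "Treatment D (Day 1 dosing) compared with Treatment C [Part 2". None of these sections excludes AUC0-inf from that comparison.

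The two arms of the comparison are sampled for different lengths of time. For Treatment C, section 10.1 says "On Day 1 of Period 1, a single oral dose of LOXO-292 will be administered followed by PK sampling for 168 hours". For Treatment D on Day 1 it says "Pharmacokinetic sampling for LOXO-292 will be taken for 24 hours following LOXO-292 dosing on Day 1".

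Section 13.3.2 adds a caveat: "The sampling to 24 hours for Day 1 PK in Period 2, Part 2 may not be sufficient for calculation of several Kel-dependent PK parameters". It calculates parameters only where appropriate and reports no Kel, AUC0-inf or half-life when a profile shows no terminal log-linear phase. Three points are enough for the fit.

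**The concern.** The endpoint sections and the caveat in 13.3.2 do not agree: a parameter that the protocol doubts can be obtained on Day 1 is still primary for Day 1. The protocol has also met this problem before. On the patient data, section 8.1.1 says "Although the pharmacokinetic sampling of LOXO-292 was not long to adequately characterize AUC0-inf, the half-life was estimated to be at least 12 hours or longer". Section 8.2.2 defends the 24 h window because P-gp acts mainly during absorption and distribution. That argument supports AUC0-24 and Cmax, not an extrapolation to infinity.

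This comparison is meant to detect an increase in exposure from acute P-gp inhibition. A primary ratio with a large extrapolated tail on one side only is imprecise. Under some disposition profiles it would also be pulled in the direction that masks an increase.

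**Working it through.** **Inputs from the protocol.** Half-life 12 to 30 h (8.2.1: "LOXO-292 exhibits a half-life of at least 12 hours", and possibly as "long as 30 hours after a single dose; PK sampling will therefore be done up to 168 hours"); three to five half-lives regarded as adequate for total exposure (8.2.1); Tmax about 2 h (8.1.1); linear trapezoid and AUC0-inf = AUC0-t + Clast/Kel (13.3.2); sampling times from the Part 2 flow chart.

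**Reproducing the plan's own figure.** Period 1 has 20 PK samples (0-168 h), Period 2 Day 1 has 14 (0-24 h) and Day 10 has 20. 20 + 14 + 20 = 54, or 53 if the 168 h and Day 1 predose draws are shared. This matches the 53 up to 54 in section 13.5.2 and confirms the short Day 1 profile.

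**Coverage.** 24/12 = 2.0 half-lives, 24/24 = 1.0 and 24/30 = 0.8. Even the lower end of the protocol's yardstick, 3 half-lives, would need 36 to 90 h.

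**Fraction beyond 24 h, one-compartment oral model.** With k = ln 2/half-life and ka chosen so that ln(ka/k)/(ka − k) = 2 h, the fraction is [ka·exp(−24k) − k·exp(−24ka)]/(ka − k). At 12 h: k = 0.0578, ka = 1.77, giving 1.77 × 0.250/1.711 = 25.8%. At 30 h: k = 0.0231, ka = 2.33, giving 2.33 × 0.574/2.307 = 58.0%. The values at 18 and 24 h are 40.5% and 50.7%.

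**Precision.** With an assumed 10% error per sample, the SD of ln AUC0-inf from a 24 h profile is 0.07, 0.25 and 0.38 at half-lives of 12, 24 and 30 h.

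**Bias with no interaction (true ratio 1.00).** AUC0-inf is computed without noise at the protocol's times. Day 1 uses 0-24 h with Kel from 8, 12 and 24 h; Treatment C uses 0-168 h with Kel from the late points.

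| Disposition | AUC0-inf ratio |
|---|---|
| One-compartment, 12 to 30 h | 0.96 to 0.99 |
| Two-phase (assumed), terminal 12 h | 0.93 to 0.95 |
| Two-phase (assumed), terminal 24 or 30 h | 0.75 to 0.91 |

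The two-phase rows assume ka 1.5/h, a first-phase half-life of 4 to 8 h and a terminal weight of 10% to 50%. None of these comes from the documents. In the one-compartment row the Day 1 slope is correct, and the small shortfall comes from the linear trapezoid over Treatment C's 24 h intervals.

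**Would the log-linear rule catch it?** On the 24 to 30 h two-phase grid, the Day 1 apparent half-life is about 7 to 18 h, yet the r-squared of the three-point fit is at least 0.986 throughout. The apparent extrapolated fraction is only 9% to 40%, because a slope that is too steep shrinks its own tail.

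**Example.** First phase 4 h, terminal 24 h, intercept ratio 3: apparent half-life 11.0 h, true extrapolated fraction 35.7%, apparent 21.1%, ratio 0.806. A true bioavailability ratio of 1.25 would read 1.25 × 0.806 = 1.01. AUC0-24 over the same window in both treatments returns 1.25.

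**The case against.** The protocol partly handles this. Section 13.3.2 contains the caveat and the log-linear rule, AUC%extrap is itself a reported parameter, and AUC0-24 and Cmax stand beside AUC0-inf for the same comparison. The protocol sets no equivalence bounds or decision rule, so no conclusion turns on AUC0-inf alone. Acceptance rules for Kel and a ceiling on extrapolation usually belong in the SAP, which is not shown and may contain them.

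Much of this stands, and it limits the point. A reader might infer that 24 h can never yield AUC0-inf. The documents do not say so: a value can be computed whenever the last points look log-linear, and the protocol only doubts that it will be adequate. A reader might also infer that the ratio is biased downward as a matter of course, or that it would reverse a true increase. That needs a distribution phase lasting past about 8 h, and no section describes one. The direction is not fixed either: a transient clearance effect fading with rifampin's 3.35 h half-life gives a bias of −3.3% to +1.2%, and slow absorption (Tmax 7.6 to 10.3 h, unlike the stated 2 h) gives ratios of 1.04 to 1.34. Nor is it known that Day 1 repeats the earlier patient sampling window, since its length is not given.

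The objection does not remove the conflict between sections. The primary endpoints are fixed in the protocol, and section 14.3 requires an amendment for major changes to them or their analysis. This is therefore more than SAP detail.

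**Conclusion.** The point holds as an unreliable primary endpoint for one comparison. On the protocol's own half-life range and Tmax, with one-compartment disposition, 26% to 58% of Day 1 AUC0-inf would be extrapolated from 0.8 to 2 half-lives of data. The reference is observed to 168 h, and the protocol's own caveat is not carried into its endpoint and analysis sections.

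Bias is a conditional second step. It is slight (0.96 to 0.99) for one-compartment disposition and reaches 0.75 to 0.91 only on the assumed two-phase grid with a 24 to 30 h terminal half-life. In that setting the stated log-linear rule would not reliably withhold the value, and an extrapolation ceiling could miss it too. The Part 1 comparison and the Day 10 comparison are unaffected, because both arms there are sampled to 168 h.

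**What to change.** In sections 8.2.3, 9.2, 14.3.1.2 and 14.3.1.3, state that:

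- the primary Treatment D (Day 1) vs C comparison rests on Cmax and on AUC0-24, with AUC0-24 derived over the same 0-24 h window for Treatment C in Period 1;
- AUC0-inf and the other Kel-dependent parameters (Kel, half-life, CL/F) for Period 2 Day 1 of Part 2 are omitted, or listed descriptively with AUC%extrap and not compared;
- AUC0-t is not compared between Day 1 and Treatment C over unequal windows. This is a separate defect: 0-24 h against up to 0-168 h pushes that ratio down whatever the disposition;
- AUC0-inf is kept for Treatment C and for Treatment D (Day 10).

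No sample, visit or subject changes. The cost is a protocol amendment with matching SAP wording, and the loss of the formal Day 1 ratios for both AUC0-inf and AUC0-t. AUC0-24 and Cmax are already planned for this comparison.
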